11.3.1.10. Best Overall Response

The best overall response is the best response recorded from the start of the study treatment until the end of treatment taking into account any requirement for confirmation (achievement of both measurement and confirmation criteria, depending on the nature of the study and the protocol requirement). The patient's best overall response assignment will depend on the findings of both target and non-target disease and will also take into consideration the appearance of new lesions.

Table 11. Best overall response when confirmation of CR and PR required

Overall response First time point	Overall response Subsequent time point	BEST overall response
CR	CR	CR
CR	PR	SD, PD or PR ^a
CR	SD	SD provided minimum criteria for SD duration met, otherwise, PD
CR	PD	SD provided minimum criteria for SD duration met, otherwise, PD
CR	NE	SD provided minimum criteria for SD duration met, otherwise NE
PR	CR	PR
PR	PR	PR
PR	SD	SD
PR	PD	SD provided minimum criteria for SD duration met, otherwise, PD
PR	NE	SD provided minimum criteria for SD duration met, otherwise NE
NE	NE	NE

CR = complete response, PR = partial response, SD = stable disease, PD = progressive disease, and NE = not evaluable.

^a If a CR is truly met at first time point, then any disease seen at a subsequent time point, even disease meeting PR criteria relative to baseline, makes the disease PD at that point (since disease must have reappeared after CR). Best response would depend on whether minimum duration for SD was met. However, sometimes 'CR' may be claimed when subsequent scans suggest small lesions were likely still present and in fact the patient had PR, not CR at the first time point. Under these circumstances, the original CR should be changed to PR and the best response is PR.

In some circumstances, it may be difficult to distinguish residual disease from normal tissue. When the evaluation of a CR depends upon this determination, it is recommended that the residual lesion be investigated by fine needle aspirate or biopsy before assigning a status of CR.

For equivocal findings of progression (e.g., very small and uncertain new lesions; cystic changes or necrosis in existing lesions), treatment may continue until the next scheduled assessment. If at the next scheduled assessment, progression is confirmed, the date of progression should be the earlier date when progression was suspected.

Patients with a global deterioration of health status requiring discontinuation of treatment without objective evidence of disease progression at that time should be reported as "symptomatic deterioration" (see Study Manual specific data collection instructions). Of note, every effort should be made to document the objective progression even after discontinuation of treatment. Symptomatic deterioration is not a descriptor of an objective response: it is a reason for stopping study therapy. The objective response status of such patients is to be determined by evaluation of target and non-target disease.

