20. Tumor imaging: to be performed at screening, within 28 days from treatment start (in case a tumor imaging is already available in the specified time window, it has not to be repeated); at the end of even months (even cycles) of treatment and at EoT. The EoT assessment is to be performed only if it was not performed in the previous 4 weeks. In patients withdrawn for reasons other than progressive disease (PD), during follow up, tumor assessment should be performed every 2 months, until PD or until a new antitumor therapy starts. On treatment, a time window of -2/+5 days is allowed. Patients with responding tumors (complete or partial response) must have response confirmed by CT scan at least 4 weeks after the 1 st documentation of response. The same method of assessment and technique should be used to characterize and follow the same lesion at screening, during treatment and at EoT. Ct scan is the desirable method for lesion measurement (see Section 11.3.1).
21. BCLC and TNM Staging: TNM and BCLC staging will be requested at enrollment for all patients, including collection of clinical related additional info
22. Survival follow up: post-treatment survival status, including additional information (e.g. new anticancer therapy), will be collected at the 28-days follow up visit and thereafter every 2 months from last treatment administration until death. Telephone contacts are acceptable for these assessments.
23. Biomarkers sampling: peripheral blood samples will be collected at Enrollment (≤ 7 days before Cycle1 Day1) for analysis of selected molecular alterations in circulating free DNA (cfDNA) from plasma
24. PK blood sample: during the Phase II, a sparse sampling procedure will be adopted; blood sampling for PK is to be performed at cycles 1, 2, 3 and 4 (refer to Table 5 for details).
25. End of Treatment (EoT): visit to be performed within 7 days from the decision of discontinuing the study drug.
26. Off treatment assessments: 28 days, and no more than 35 days, after discontinuation of study treatment patients will return for the following assessments: ECOG PS, blood pressure and heart rate, hematology, blood chemistry, coagulation, concomitant medications, adverse events and survival follow up. Further follow up contacts will be scheduled every 2 months from last treatment administration, until death, to assess the survival status, including possible additional information.

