10. SUBJECT WITHDRAWAL FROM STUDY PARTICIPATION

Patients may withdraw from the study at any time at their own request, or they may be withdrawn at any time at the discretion of the Investigator or Sponsor for safety, behavioral, or administrative reasons.

If the patient does not return for a scheduled visit, every effort should be made to contact him/her. In any circumstance, every effort should be made to document patient outcome, if possible. The Investigator should inquire about the reason for withdrawal, request the patient to return for a final visit, if applicable, and follow-up with the patient regarding any unresolved adverse events.

If the patient withdraws consent for disclosure of future information, no further evaluations should be performed and no additional data should be collected. The Sponsor may retain and continue to use any data collected before such withdrawal of consent.

Patients may continue with therapy unless any of the following occurs:

- Disease progression by RECIST 1.1 at any time, unless there is reasonable evidence of clinical benefit to justify continuation on treatment, to be discussed with the Sponsor;
- Unacceptable drug-related toxicities incompatible with continuation of treatment with NMS-01940153E according to the judgment of the Investigator, even at a reduced dose;
- Any medical event requiring administration of an unauthorised concomitant treatment if it interferes with the study evaluations and/or if it jeopardises patient's safety (see Section 9.2.7);
- Change in the patient's medical status (including pregnancy) such that the Investigator believes that patient safety may be compromised or that it would be in the best patient's interest to stop treatment;
- Occurrence of permanent or significant incapacity or disability;
- Treatment delay for >1 week from day 28 of any cycle due to treatment related toxicity, unless the investigator believes treatment continuation is in the best patient's interest. In this case a maximum delay of 2 weeks is allowed;
- More than two dose de-escalations required;
- Substantial deviation from specified inclusion or exclusion criteria or non-compliance by the patient with protocol requirements;
- Patient's refusal to continue study treatment;
- Withdrawal of consent;

- Patient lost to follow up;
- Death;
- Study terminated by the Sponsor.

Patients will be withdrawn from the study in case of:

- Withdrawal of consent;
- Patient lost to follow up;
- Death;

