11.3.1. Tumor Imaging

Baseline tumor imaging (by CT scan, PET or MRI) has to be performed at screening within 28 days prior to the treatment start. On treatment, tumor assessments will be performed every even month (i.e., end of Cycle 2, 4, 6 etc) or whenever a clinical deterioration is observed and at the end of last cycle, unless a tumor assessment was performed within the previous 4 weeks. In patients withdrawn for causes other than disease progression, during follow up, regular tumor imaging assessments will be performed every 2 months, until PD or until a new antitumor therapy starts. On treatment, a time window of -2/+5 days is allowed.

Patients with responding tumors (complete or partial response) must have response confirmed at least 4 weeks after the first documentation of response.

CT scan is the desirable method for lesion measurement. MRI is acceptable provided that the size of the measurable lesion is twice the slice thickness of the MRI. MRI should be performed at pre-treatment in case of known or suspected CNS involvement.

According to RECIST, the same method and technique (CT scan or MRI) should be used to characterize each identified and reported lesion at baseline and during the following assessments.

Imaging-based evaluation should be preferred to clinical examination when both could be used to assess the antitumor effect of the treatment.

According to mRECIST, tumor assessment should be performed with the administration of intravenous contrast to obtain a dual-phase imaging of the liver. To prevent possibly allergic reactions to intravenous Contrast Medium (CM), patients with previous reaction(s) to CM, asthma even drug controlled and/or food or drug allergies will be treated with a premedication (corticosteroid).

Patients can be followed with either contrast-enhanced spiral CT (preferably with use of multi-slice scanners) or contrast-enhanced dynamic MRI. Each modality has advantages and disadvantages, and mRECIST does not recommend one modality over another.

However, it is recommended that the same imaging modality be used throughout the study. Ultrasound – including contrast-enhanced ultrasound – is not recommended for the general use of mRECIST.

PET/CT is not accepted for treatment assessment in guidelines.

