11.3.1.7. Confirmation of Tumor Response

To be assigned a status of PR or CR, changes in tumor measurements in patients with responding tumors must be confirmed ≥ 4 weeks after the criteria for response are first met by the same tumor imaging technique used at baseline and on treatment (e.g., CT scan or MRI).

In case of SD, measurements must have met the SD criteria at least once after study entry at the minimum interval of 8 weeks.

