3.2. Endpoints

3.2.1. Primary Endpoint(s)

- Drug related Dose Limiting Toxicities (DLTs) (Phase I).
- Objective Response Rate (ORR). The ORR will be calculated as the proportion of evaluable patients who have achieved, as best overall response (BOR), confirmed complete response (CR) or partial response (PR) measured by investigator-assessed RECIST 1.1 (Phase II).

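### The best overall response window ends at end of treatment with no progression cut-off, so some off-treatment confirmations fall outside it and some post-progression responses fall inside it

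*Protocol*

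**What the plan says.** Protocol Section 11.3.1.10 takes BOR as the "best response recorded from the start of the study treatment until the end of treatment taking into account any requirement for confirmation". It mentions neither progression nor new anticancer therapy as an end point of the window. SAP Sections 3.2.1 and 9.7.1 build the primary ORR on BOR without giving a window. SAP Section 9.7 refers further definitions to a separate appendix of mock-ups and algorithms, which is not among the documents reviewed.

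Four other rules bear on the window:

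- **Confirmation.** Section 11.3.1.7: "To be assigned a status of PR or CR, changes in tumor measurements in patients with responding tumors must be confirmed". Section 11.3.1 says responding patients "must have response confirmed at least 4 weeks after the first documentation of response".
- **Scan timing.** On treatment, "tumor assessments will be performed every even month (i.e., end of Cycle 2, 4, 6 etc". At end of treatment (EoT), Section 7 (Phase II schedule, tumor imaging footnote) says: "The EoT assessment is to be performed only if it was not performed in the previous 4 weeks". The EoT visit falls within 7 days of the decision to stop.
- **After treatment.** For patients withdrawn without progressive disease (PD), the same footnote says "tumor assessment should be performed every 2 months, until PD or until a new antitumor therapy starts".
- **Treatment after progression.** Section 10 lists RECIST 1.1 progression as a reason to stop, "unless there is reasonable evidence of clinical benefit to justify continuation on treatment, to be discussed with the Sponsor".

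**The concern.** The response window and the imaging plan do not match. Imaging continues after treatment until progression or new therapy, but response stops counting at end of treatment. Treatment may continue after RECIST progression, and the response window then continues with it.

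The primary endpoint could therefore be misclassified in both directions. A genuine PR may go uncounted because the patient stopped soon after it was first seen, which ties the error to toxicity. A PR recorded after progression may be counted because the patient was kept on drug, which ties the error to a discretionary decision in an open-label trial with investigator-assessed response.

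**Working it through.** **The plan's own figure.** Inputs from Protocol Section 12.1: assumed ORR 0.30, one-sided 95% lower limit, distance to the limit no more than 0.12, 10% non-evaluable. The exact (Clopper-Pearson) lower limit is L(x, n) = the 0.05 quantile of Beta(x, n − x + 1). With x = 0.3n treated as continuous, the smallest n with 0.30 − L ≤ 0.12 is 38, where the distance is 0.1197. Inflation: 38/0.90 = 42.2, rounded up to 43. The plan's 38 and 43 are reproduced.

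**Case 1: response confirmed only off treatment.** Take a patient with no delay before the end of cycle 2.

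- First PR at the end of cycle 2: day 56. Earliest confirmation: 56 + 28 = day 84.
- Suppose cycle 3 cannot start and the patient comes off at the longest permitted delay, 2 weeks: 56 + 14 = day 70. Latest EoT visit: 70 + 7 = day 77.
- Gap from scan to EoT: 77 − 56 = 21 days, under 4 weeks, so no EoT scan is required. Moving the scan across its −2/+5 day window gives gaps of 23 to 16 days.
- The next scheduled scan is the two-monthly follow-up scan. The documents do not say what the two months are counted from. Taking 60 days from the last dose (cycle 2 day 15 = day 43), from the scan (day 56) or from EoT (day 77) gives day 103, 116 or 137.
- Each of these is later than day 84, so the scan could confirm the PR. Each is also after end of treatment, so it lies outside the literal window.

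If EoT falls 4 weeks or more after the first PR scan, an EoT scan is required and can confirm the response. Case 1 is therefore confined to stops without PD and with a gap under 4 weeks.

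**Case 2: response after progression.** Section 11.3.1.4 measures PR against the baseline sum and PD against the smallest sum on study. Illustrative target sums at 8-week intervals:

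| Week | Sum (mm) | From baseline | From smallest sum | Reading |
|---|---|---|---|---|
| 0 | 100 | – | – | baseline |
| 8 | 65 | −35% | – | PR |
| 16 | 80 | −20% | +23.1%, +15 mm | PD |
| 24 | 68 | −32% | +4.6%, +3 mm | PR |
| 32 | 66 | −34% | +1.5%, +1 mm | PR, 8 weeks later |

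If treatment continues beyond week 16, the last two scans are on drug and inside the window. Table 11 sends the week 8 and 16 pair (PR, PD) to stable disease or PD. It sends a PR–PR pair to PR. It has no row beginning with PD and no statement that pairs after PD are ignored. If PD came from a new lesion that persists, Table 9 keeps the overall response at PD, so this route does not open.

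**What one patient is worth.** 1/38 = 2.6 percentage points. Exact lower limits:

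| Responders/38 | One-sided 95% | Two-sided 95% |
|---|---|---|
| 11 | 17.2% | 15.4% |
| 12 | 19.3% | 17.5% |
| 13 | 21.6% | 19.6% |

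The 18% reference is crossed between 11 and 12 responders with the one-sided limit used for sample size. It is crossed between 12 and 13 if the 95% interval in SAP Section 9.7.1 is two-sided.

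**Sensitivity to assumed shares.** The documents give no frequency for either case, so the shares below are assumptions. The entry is the probability of at least 12 responders in 38.

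- True ORR 0.30, with a share of responders lost through case 1: 0.476 at 0%, 0.396 at 5%, 0.317 at 10%, 0.181 at 20%.
- True ORR 0.18, with points added through case 2: 0.031 at 0, 0.044 at 1, 0.062 at 2, 0.085 at 3.

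**The case against.** The strongest reply is that this is loose wording with little reach.

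- The EoT scan confirms many early stoppers. This stands. A reader might infer that any responder who stops early for toxicity goes unconfirmed, but the imaging footnote does not support that.
- The confirmation rules set a minimum interval and a consistent technique. None says the confirming scan must be on treatment, so a PR seen on drug and confirmed in follow-up could fairly be counted. That reading is available, but it competes with a window that ends at end of treatment. A primary endpoint should not rest on that choice.
- Progression is the default stop. Continuing needs evidence of clinical benefit and sponsor discussion, and a persisting new lesion blocks a later response. This also stands: case 2 is the narrower of the two.
- Losing responses makes ORR conservative. That is true of case 1 alone; case 2 acts the other way, and the net direction is unknown.
- The separate appendix may hold a BOR algorithm. It may, but if it differs from Section 11.3.1.10 the two would conflict on the primary endpoint.
- One patient near 18% might look like a pass or a fail. The documents do not support that reading: Section 12.1 calls 18% a meaningful lower bound within a precision calculation, and no success rule is attached to it.

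A reader might also infer that the present window admits responses after new anticancer therapy. Section 9.2.7.6 bars other anticancer treatment during study treatment, so that cut-off matters only once follow-up scans are included.

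**Conclusion.** The point holds in limited form. The only stated BOR window closes at end of treatment and has no progression cut-off. Taken literally, it excludes a scheduled confirming scan in patients who stop without PD less than 4 weeks after their first PR scan. It also leaves open a PR–PR pair after target-lesion progression in patients kept on drug.

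Each affected patient moves ORR by 2.6 points at n = 38. How many will be affected cannot be derived from the documents, and the probabilities above rest on assumed shares. The conclusion also assumes that the unseen appendix does not already set a different window; if it does, the documents need reconciling instead. This should be settled before the response data are analysed. It does not invalidate the design or the sample size.

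**What to change.** In Protocol Section 11.3.1.10 and SAP Section 9.7.1, define BOR as the best response, with CR and PR confirmed at least 4 weeks later, over assessments from first dose to the earlier of documented progression or start of new anticancer therapy. If neither occurs, the window ends at the last evaluable assessment. State that assessments count equally on or off study drug, that a scheduled post-treatment scan can confirm a response, and that scans after progression do not count. Add the last statement as a note to Table 11.

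Use RECIST 1.1 progression for the RECIST ORR and mRECIST progression for the mRECIST ORR (SAP Section 9.7.2). The two can differ, because mRECIST progression is judged on viable enhancing tumor. Bring the algorithms appendix into line.

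The cost is a sentence or two in each document and a check of the programmed derivation. The scans are already scheduled, treatment rules are untouched, and the sample size stays at 38 evaluable (43 with inflation).

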11.4. Outcomes Research Assessments

Not applicable.

11.5. Safety Assessments

Safety assessments include collection of AEs, SAEs, 12-lead ECGs, pregnancy tests, vital sign measurements, physical examinations and safety laboratory tests as outlined in the Schedule of events, Section 7.

Additional safety assessments may be performed if deemed necessary by the Investigator.

Assessment of adverse events will include type, incidence, severity (graded by the National Cancer Institute [NCI] Common Terminology Criteria for Adverse Events [CTCAE], Version 5.0) [21], timing, seriousness, and relatedness.

11.5.1. Adverse Event Assessment

11.5.1.1. Definition of Adverse Events

11.5.1.1.1. Adverse Event

According to ICH definition and EU Regulation (No. 536/2014), an AE is defined as any untoward medical occurrence in a subject to whom a medicinal product is administered and which does not necessarily have a causal relationship with this treatment. An adverse event can therefore be any unfavorable and unintended sign (e.g., an abnormal laboratory finding), symptom, or diagnosis temporally associated with the use of a medicinal product, whether or not considered related to the medicinal product.

Any untoward medical occurrence, which occurs outside the period of patient follow-up defined in the protocol, is not considered an AE. Symptoms or medically significant laboratory or instrumental (e.g., by electrocardiography) abnormalities of a pre-existing condition should not be considered an AE. However, occurrence of new symptoms, laboratory or instrumental abnormalities, as well as worsening of pre-existing ones, is considered AEs.

11.5.1.1.2. Serious Adverse Events

A serious adverse event (SAE) is any untoward medical occurrence that at any dose falls into one or more of the following categories:

- Results in death
- Is life-threatening, i.e., an event which, in the view of the Investigator, placed the patient at risk of death at the time of event (it does not include an event which hypothetically might have caused death if it was more severe)
- Requires inpatient hospitalization or prolongation of existing hospitalization

- Results in persistent or significant disability/incapacity, where disability is defined as a substantial disruption of a person's ability to conduct normal life functions, either reported or defined as per clinical judgment
- Is a congenital anomaly/birth defect (if exposure to product just before conception or during pregnancy resulted in an adverse outcome in the child)
- Is any other important medical event, i.e., may not result in death, be life-threatening, or require hospitalization, but based upon appropriate medical judgment, it may jeopardize the patient and may require medical or surgical intervention to prevent one of the outcomes listed in the points above. Examples of such events include allergic bronchospasm requiring intensive treatment in an emergency room or at home, and blood dyscrasias or convulsions that do not result in inpatient hospitalization.

A non-serious adverse event is any adverse event that does not meet the criteria listed above or the outcome cannot be determined with the information provided.

Each adverse event has to be classified by the Investigator as serious or non-serious.

In this study the following do not have to be classified as SAEs:

- Admission to hospital required by protocol.
- Hospitalization for routine treatment or monitoring of the studied indication not associated with any deterioration in patient's clinical condition.
- Hospitalization or prolongation of hospitalization for technical, practical, or social reasons, in absence of an AE.
- A procedure requiring hospitalization planned prior to starting the study treatment; must be documented in the Source Documents and the e-Case Report Form (e-CRF). Prolonged hospitalization for a complication remains a reportable SAE.
- Hospitalization for an elective treatment of a pre-existing condition unrelated to the studied indication.
- Events definitely related to disease progression.

However, all deaths occurring during the reporting period have to be reported as SAEs, even if due to disease progression.

